4.3.5 Electrocardiogram (ECG)

Safety ECG measurements will be collected throughout the study. Baseline ECG values are those collected at Visit 2 (Day 0) prior to the first dose of IP.

ECG parameters include heart rate, PR interval, RR interval, QRS interval, QT (uncorrected) interval, QTcF interval, and QTcB interval. In addition, the overall interpretation of the investigator will be documented as normal, abnormal but not clinically significant (NCS), or abnormal and clinically significant (CS). All clinically significant abnormal findings will be reported as AEs also. Absolute values and change from baseline in post-baseline values will be summarized by study part (Part A and Part B). By-patient listings of ECG data and overall interpretations collected during Part A and Part B will be provided.

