7.7.5. ECG

Electrocardiograms will be performed to collect the electrical activity of the heart throughout the study to monitor safety. An evaluation of normal by a physician must be obtained before the patient is enrolled in the treatment period.

Electrocardiograms will be performed at Visit 2 (baseline), Visit 3 (Week 1), Visit 4 (Week 5), and Visit 5 (Week 12) in the treatment period (Part A), and will be assessed at Visit 7 (Week 28) and the Final OLE Visit or Taper Visit in the OLE period (Part B).

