8.1.5. Clinical Laboratory and Other Safety Evaluations

A change in the value of a clinical laboratory, vital sign, ECG assessment can represent an AE if the change is clinically significant or if, during treatment with the IP, a shift of a parameter is observed from a normal value to an abnormal value, or there is a further worsening of an already abnormal value. When evaluating such changes, the extent of deviation from the reference range, the duration until return to the reference range (either while continuing treatment or after

the end of treatment with the IP), and the range of variation of the respective parameter within its reference range must be taken into consideration.

If, at the end of the treatment period, there are abnormal clinical laboratory, vital sign, or ECG values that were not present in the pretreatment findings observed closest to the start of study treatment, further investigations should be performed until the values return to within the reference range or until a plausible explanation (e.g., concomitant disease) is found for the abnormal values.

The investigator should decide, based on the above criteria and the clinical condition of a patient, whether a change in a clinical laboratory, vital sign, or ECG parameter is clinically significant and therefore represents an AE.

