2 STATISTICAL CONSIDERATIONS

2.1 GENERAL CONSIDERATIONS

Statistical analyses will be performed using SAS System, Version 9.4 or higher (SAS Institute, Inc., Cary, NC).

No formal hypothesis testing will be performed for this study. Data will be summarized descriptively. Separate summaries will be presented for data collected in Part A and data collected in Part B of the study. Unless otherwise specified, descriptive statistics for continuous variables will include number of non-missing observations (n), arithmetic mean, standard deviation (SD), 25th and 75th percentiles, minimum, median and maximum. For categorical variables, descriptive statistics including counts and percentages will be used. Only observed data will be summarized. Missing data will not

be imputed. Scheduled assessments will be included in summaries with the exception of reports of abnormal laboratory, vital sign, or ECG values.

Study data from all assessments (scheduled and unscheduled) will be displayed in individual data listings by study part (Part A or Part B), patient and visit, if applicable.

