3.2 ANALYSIS VISIT WINDOWS

Efficacy Analyses

Efficacy analyses will use data only from scheduled visits. Data will be reported by designated visit.

Data collected at unscheduled visits will be provided in listings.

For analysis of data collected across specific study periods, the following definitions will be applied:

- Baseline period: Visit 1 to Visit 2; Study Week -4 (Day -32 ± 4) through Study Day 0 (date of first dose of IP)
- Titration period: Visit 2 + 1 day to Visit 4; Study Day 1 through Study Week 4 (Day 28 ± 3 days; date of Visit 4)
- Maintenance period: Visits 4 + 1 day and 5; Study Week 5 (± 3 days) through Study Week 12 (± 3 days)
- 12-week treatment period: titration period + maintenance period (including taper and safety visits if not continuing in OLE)
- OLE period if continuing in OLE: Visit 5 + 1 day through final visit

Safety Analyses

Safety data will be summarized by actual visit. No visit windowing will be applied.

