4.3.2.2 Incidence of TEAEs

The number and percentage of patients reporting at least one TEAE during Part A, Part B and overall will be summarized by MedDRA System Organ Class (SOC) and preferred term (PT). The summary will be sorted by descending frequency within SOC and PT within SOC.

A detailed listing of AEs for each patient will be provided. The listing will include the

verbatim term reported by the Investigator, MedDRA SOC and PT, onset date/time, end date/time, severity, seriousness (yes/no), seriousness reason, relationship to study drug, action taken, withdrawal from study, treatment required, and outcome.

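### ECG interpretations are only listed and no per-patient QTcF count is planned, so abnormal readings and QTc rises not reported as adverse events are not counted

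*SAP*

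**What the plan says.** ECG is a listed safety endpoint for both parts (SAP 1.2.4). Protocol 7.7.5 sets the Part A schedule: "Electrocardiograms will be performed at Visit 2 (baseline), Visit 3 (Week 1), Visit 4 (Week 5), and Visit 5 (Week 12"). In Part B, ECGs are due at Visit 7 and at the final or taper visit.

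SAP 4.3.5 collects heart rate, PR, RR, QRS, QT, QTcF and QTcB, plus an overall reading of normal, abnormal NCS or abnormal CS. It plans three things:

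- Numerical summaries: "Absolute values and change from baseline in post-baseline values will be summarized by study part (Part A and Part B").
- Listings: "By-patient listings of ECG data and overall interpretations collected during Part A and Part B will be provided".
- A link to adverse events: "All clinically significant abnormal findings will be reported as AEs also".

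Two general rules also apply. SAP 3.2 states: "Safety data will be summarized by actual visit. No visit windowing will be applied". SAP 2.1 makes quartiles, minimum and maximum part of the default statistics. It restricts summaries to scheduled assessments, with an exception for "reports of abnormal laboratory, vital sign, or ECG values".

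**The concern.** The primary objective includes preliminary safety. For an ECG parameter such as QTcF, the useful safety question is usually how many patients had a high value or a large increase, and the planned outputs do not answer it. The three-level reading is collected but never tabulated, and no patient-level QTcF category is planned.

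The adverse event tables cover only what the investigator reports as an event. A change read as NCS, or a QTcF rise not judged significant, can pass through the report without entering any number of patients. If it occurred on an unscheduled ECG, it would not appear in the summary maximum either.

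**Working it through.** The documents give no figure on this point, so there is none to reproduce. The check is mainly a comparison of sections, followed by a short illustration.

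**1. How similar data are handled in the SAP**

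| Data | Count or shift table planned? |
|---|---|
| Laboratory (4.3.3) | Yes: shift from baseline to worst post-baseline class, and a listing of out-of-range values |
| Physical examination (4.3.4.2) | Yes: counts and percentages of abnormal changes |
| Neurological examination (4.3.4.3) | Yes: number and percentage abnormal |
| Developmental examination (4.3.4.4) | Yes: number and percentage abnormal |
| ECG interpretation (4.3.5) | No: listing only |
| QTcF by patient (4.3.5) | No: numerical summary and listing only |

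The three examinations use the same normal/NCS/CS scale as the ECG.

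**2. What the adverse event route captures.** CS findings become adverse events, and SAP 4.3.2.2 counts patients with such events at both MedDRA coding levels: "The number and percentage of patients reporting at least one TEAE during Part A, Part B and overall will be summarized by MedDRA System Organ". For other changes, Protocol 8.1.5 says a change can be an adverse event "if, during treatment with the IP, a shift of a parameter is observed from a normal value to an abnormal value", but it leaves the decision to the investigator. An NCS shift may therefore be reported, but need not be.

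**3. What the summary statistics capture.** Take 30 patients and an assumed QTcF increase of 60 ms. This value is for illustration and is not a proposed limit.

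- One patient: the visit mean moves by 60/30 = 2 ms and the maximum is 60 ms.
- Two patients: the mean moves by 120/30 = 4 ms and the maximum is still 60 ms.
- About a quarter of patients (0.25 × 30 = 7.5, so about seven) lie above the upper quartile, which does not show how large their increases are.

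The maximum reveals that a large change occurred. It does not say in how many patients.

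**4. Unscheduled ECGs.** Under SAP 2.1 these stay out of the summaries, including the maximum. The one exception is reports of abnormal values, and SAP 4.3.5 defines no such report for ECGs. Protocol 7.3.5 makes visits after Visit 8 unscheduled, up to six months apart, with assessments at the investigator's discretion. Any ECG taken then is affected. The SAP was written for a 24-week extension, whereas the current protocol lets Part B run until marketing or termination.

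**5. What a count would tell.** If a fraction p of patients truly has an outlying ECG, the chance of at least one among 30 is 1 − (1 − p)^30:

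| Assumed p | Chance of at least one |
|---|---|
| 1% | 26% |
| 3% | 60% |
| 5% | 79% |
| 10% | 96% |

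If none of 30 is affected, the one-sided 95% upper bound is 1 − 0.05^(1/30) = 9.5%. A count, even of zero, is a result that can be reported; a listing does not give it directly.

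**The case against.** Several points on the other side are sound.

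- Protocol 9.7 asks only for descriptive statistics with changes from baseline for ECGs. It assigns numbers and percentages with abnormalities to the physical, neurological and developmental examinations. The SAP delivers what the protocol requires, and vital signs have no outlier count either.
- Protocol 7.7.5 requires a normal ECG evaluation before the treatment period. If that is followed, the shift table has a single baseline row, and every abnormal entry in the listing is itself a shift. With 30 patients and three post-baseline Part A ECGs there are at most 90 readings, which a reviewer can scan.
- Table templates are in a separate document (SAP section 8), so an abnormal-ECG report may be planned there.
- The protocol's background section reports no clinically significant ECG trend in the programme.

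These points lower the priority but do not close the gap. A short listing still leaves the reader to do the counting. A single baseline row makes the table simpler, not useless. The SAP text in hand does not define the report that SAP 2.1 mentions.

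A reader might also infer from the phrase about study part that Week 1 ECGs, taken during titration, are averaged with Weeks 5 and 12 and dilute any dose-related effect. The documents do not support that. SAP 3.2 requires safety summaries by actual visit, and SAP 2.1 splits summaries by part. Read together, they give Part A and Part B tables with visit rows, in which nothing is diluted. Section 4.3.5 merely omits the words by visit, which the laboratory and vital sign sections state.

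**Conclusion.** The point holds as a gap in tabulation. The SAP plans no count of ECG interpretations and no count of patients by QTcF value or increase. Abnormal readings and QTc rises are not counted unless reported as adverse events. Those found on unscheduled ECGs are also missing from the summary maximum.

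It would be too strong to infer that such changes are never counted or that a single large rise is hidden. CS findings enter the adverse event tables, an NCS shift may be reported as an event, and a large change on a scheduled ECG appears as the maximum.

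The size is modest. No efficacy result is affected, all the data are collected, and the listings would contain the individual values. The conclusion rests on reading SAP 2.1 as keeping unscheduled ECGs out of summaries, and on the separate table templates not already supplying these counts. The 60 ms value and the outlier rates are assumptions for illustration.

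**What to change.** In SAP 4.3.5:

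1. Add a table of overall interpretation (normal, NCS, CS) from baseline to worst post-baseline reading, by study part and including unscheduled ECGs.
2. Add the number and percentage of patients by maximum post-baseline QTcF and by maximum increase from baseline, also including unscheduled ECGs. The sponsor should state the limits before database lock.
3. Add the words by visit to the summary sentence, so that it agrees with SAP 3.2.

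The cost is a change of SAP wording and two small tables from data already collected. The only downside is slightly more output.

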4.3.6 Other Safety Analysis

4.3.6.1 Columbia-Suicide Severity Rating Scale (C-SSRS)

The C-SSRS suicidal behavior and suicidal ideation scores recorded at baseline and any changes in post-baseline scores from the previous visit will be summarized descriptively by visit, including the number and percentage of subjects reporting any suicidal behavior and any suicidal ideation as defined in Table 5. Adult and pediatric C-SSRS data will be

summarized separately.

C-SSRS data collected, including scores for suicidal ideation, intensity of ideation and actual suicide attempts, will be listed by patient and visit.

Table 5: C-SSRS Categories for Analysis

Category	C-SSRS Item response is “YES”
Suicidal behavior	Preparatory acts or behavior Aborted attempt Interrupted attempt Actual attempt Complete suicide
Suicidal ideation	Wish to be dead Non-specific active suicidal thoughts Active suicidal ideation with any methods (not plan) without intent to act Active suicidal ideation with some intent to act, without specific plan Active suicidal ideation with specific plan and intent
Non-suicidal self-injurious behavior	Non-suicidal self-injurious behavior

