k.	Concomitant AEDs or their dose must be stable for 1 month prior to screening and cannot be changed at any time prior to Visit 4, but may be adjusted during Part B.										
l.	Caregiver given seizure and medication diary and instructions for use.										
m.	During the baseline visit, the investigator and parent/caregiver/LAR will decide on a domain and identify the specific behavior that the patient exhibits that denotes the domain. This behavior will be used at subsequent visits to assess change after the initiation of IP.										
n.	Patients who discontinue IP early will be encouraged to continue with all procedures and scheduled visits.										
o.	The 4 weeks between Screening Visit and Baseline Treatment Visit can be no less than 28 days and no more than 32 days.										
p.	Only for patients who do not continue into Part B. This will occur after 2 weeks of taper and 2 weeks after completion of treatment.										
q.	Only for patients \geq 7 years old if appropriate. Otherwise clinical judgment will be used.										
r.	Only for patients that were Screened without previous genetic testing results and had a genetic test performed at the sponsor's designated lab.										

Table 1: Schedule of Assessments - Part A

WEEK	Part A										
	Screen/Baseline		Titration and Maintenance								
-4 (Screening Visit – Start of Baseline)	0 (Baseline Treatment Visit)	Day 1	Day 2	Day 3	1	2, 3, 4	5	9	12	16 Taper/Safety Visits ^p	
Visit Windows	+ 4 days			± 1 day	± 3 days	± 3 days	± 3 days	± 3 days	± 3 days	± 3 days	
VISIT	Visit 1 ^a	Visit 2 ^o	Phone Follow-up	Phone Follow-up	Phone Follow-up	Visit 3	Phone Follow-up	Visit 4	Phone Follow-up	Visit 5	Visit 5a

s. Review of medical history only.

t. Developmental examination is limited to pediatric patients 2 to 17 years of age, inclusive.

Table 2: Schedule of Assessments - Part B

Part B								
	Final Part A Visit/ First Part B Visit	Open-Label Extension (Visits will be every 8 weeks with a telephone follow-up in-between)					Final OLE Visit or Taper Visit	Safety Follow-up Post-taper
WEEK	12	16	20	24	28	32	36 or early D/C	2 weeks post last dose
Visit Windows		± 7 days	± 7 days	± 7 days	± 7 days	± 7 days	± 7 days	± 3 days
VISIT	Visit 5	Phone follow-up	Visit 6	Phone follow-up	Visit 7	Phone follow-up	Visit 8 (Week 36) ^g or Visit X (early D/C)	Visit X
Confirm patient is “OLE eligible” (≥ 35% reduction in seizure frequency)	X							
Vital signs (BP, HR, RR, and body temperature)	X		X		X		X	X

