9.7. Safety Analyses

Safety will be reported for all patients. The results in Part A and Part B will be summarized separately and then the combined results in Part A and Part B will be summarized together. Adverse events will be tabulated by overall, system organ class, and Preferred Term using the Medical Dictionary for Regulatory Activities (MedDRA) coding system. Incidence and percentage of AEs will be presented. Additional tables, with AEs classified by severity and by only those related to drug as assessed by the investigator will be presented. Subset listings will be produced for AEs that cause withdrawal and for SAEs. Clinical laboratory tests (hematology, chemistry and urinalysis), vital signs (temperature, BP, pulse rate), weight, and ECGs will be summarized using descriptive statistics including changes from baseline. Change in C-SSRS scores where applicable will be determined. Physical, neurological and developmental examinations will be summarized using number and percentage of patients with abnormalities.

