2.2 ANALYSIS SETS

Analysis sets for this study are defined as:

- Screened population: all patients who have signed informed consent for the study.
- Safety population: all patients who have received at least one dose of GNX
- Intent-to-treat (ITT) population: all patients who receive at least one dose of GNX and have at least one post-baseline efficacy assessment.
- Per-protocol (PP) population: includes all ITT patients without major protocol violations, as will be defined prior to database lock. Patients that fall below 80% compliance at two consecutive visits during the maintenance period (i.e. Visits 4 and 5, Weeks 5 and 12) will not be included in the PP population.
- Open-label extension (OLE) population: includes all ITT patients who participate in the OLE (Part B) of the study and receive at least one dose of GNX in the Part B.
- Pharmacokinetic (PK) population: all ITT patients who have had at least one PK sample collected and a valid bioanalytical result obtained. Pharmacokinetic data collected from this population may be reported separately.

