4.3 SAFETY ANALYSIS

Safety analyses will be based on all patients in the Safety population, unless otherwise indicated. Data will be summarized for Part A, Part B and across the entire study for those patients participating in both parts.

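### SAP 4.3.6.1 measures C-SSRS change against the previous visit, so change rows after onset mislead and no table shows worsening from the pre-dose baseline

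*SAP*

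**What the plan says.** SAP 4.3.6.1 summarizes the baseline C-SSRS behavior and ideation scores. For later ratings it says that "changes in post-baseline scores from the previous visit will be summarized descriptively", by visit, and the sentence goes on: "including the number and percentage of subjects reporting any suicidal behavior and any suicidal ideation as defined in Table 5". Adult and pediatric data are summarized separately. The section ends with a listing: "C-SSRS data collected, including scores for suicidal ideation, intensity of ideation and actual suicide attempts, will be listed by patient and visit". Protocol 9.7 is less specific and names no reference point: "Change in C-SSRS scores where applicable will be determined".

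The baseline form is completed at Visit 2, before dosing (Protocol Table 1 and 7.2.2). The since-previous-visit form is used at Visits 4 and 5, at Visit 5a for patients who do not enter Part B, and at Visits 6, 7 and 8 in Part B. No C-SSRS is scheduled at Visit 3.

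SAP 3.1.1 makes the last pre-dose value the baseline for safety assessments unless a section says otherwise. SAP 4.3.3 (laboratory values), 4.3.4.1 (vital signs) and 4.3.5 (ECG) all summarize change from baseline.

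On population, SAP 4.3 says: "Safety analyses will be based on all patients in the Safety population, unless otherwise indicated". SAP 2.2 defines that set as follows: "Safety population: all patients who have received at least one dose of GNX". Section 4.3.6.1 names no other denominator. Footnote q to Protocol Table 1 limits the scale to patients of at least 7 "years old if appropriate. Otherwise clinical judgment will be used". Entry is from age 2 (Protocol 4.1, inclusion criterion 2).

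**The concern.** Preliminary safety is part of the primary objective, and the C-SSRS is a listed safety endpoint (SAP 1.2.4). The question it should answer is whether a patient became worse on ganaxolone than before it. A previous-visit difference answers that only at the first on-treatment rating. After that it compares one on-drug rating with another. Ideation that emerges and stays appears as no change, and ideation that emerges and only partly recedes appears as improvement.

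No other planned C-SSRS summary supplies the comparison. The by-visit percentages do not link a patient's later report to that patient's own baseline. No worst on-treatment category is set against baseline, and there is no C-SSRS counterpart to the starts-or-worsens rule that SAP 4.3.2 applies to adverse events. SAP 4.3 asks for safety summaries for Part A, Part B and the whole study, but visit-to-visit differences give no per-patient result for any of those periods.

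**Working it through.** The plan gives no figure to reproduce here, and its 30 patients were not derived statistically. The check applies the two reference rules to the same records.

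**Inputs.** The visit schedule is from Protocol Tables 1 and 2. The ideation scale is an assumption: 0 for none, then 1 to 5 for the five ideation items in the order of SAP Table 5. The records are illustrative.

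**Two readings of the text.** The SAP does not define how change is computed, so I take it as a difference of scores. Because Visit 3 has no C-SSRS, I take the previous visit for Visit 4 to be Visit 2, the last one with a rating.

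**Formulas.** SAP rule: score at this visit − score at the previous rated visit. Baseline rule: score at this visit − score at Visit 2.

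**Part A.**

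| Record (V2, V4, V5) | SAP rule, Week 5 | SAP rule, Week 12 | Baseline rule, Week 5 | Baseline rule, Week 12 |
|---|---|---|---|---|
| (0,4,4) | 4 − 0 = +4 | 4 − 4 = 0 | 4 − 0 = +4 | 4 − 0 = +4 |
| (0,4,2) | 4 − 0 = +4 | 2 − 4 = −2 | 4 − 0 = +4 | 2 − 0 = +2 |

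Both rules show the onset at Week 5. At Week 12 both patients are worse than before treatment, yet the SAP rule reports no change for one and improvement for the other.

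**Continuing into Part B (Visits 2, 4, 5, 6, 7, 8).**

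- Scores 0,3,3,3,3,3: SAP rule +3, 0, 0, 0, 0; baseline rule +3, +3, +3, +3, +3.
- Scores 0,4,3,2,2,2: SAP rule +4, −1, −1, 0, 0; baseline rule +4, +3, +2, +2, +2.

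In each sequence four of the five on-treatment change values are zero or negative under the SAP rule, although the patient is above baseline at all five visits.

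**What the other planned outputs show.** In all four records the patient counts as having any ideation at every on-treatment visit, and every score is in the listing. So the presence of ideation is reported. Its relation to the patient's own baseline has to be worked out by hand from the listing.

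**The case against.** The strongest reply is that nothing is concealed. The same sentence that sets the previous-visit reference also plans by-visit counts and percentages of any ideation and any behavior. All data are listed by patient, and the trial has about 30 patients. Part A has only two scheduled on-treatment C-SSRS visits before Visit 5a, and the first shows the increase. All of this stands. A reader might infer that the SAP hides ideation that emerges and persists; the documents do not support that.

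Second, Protocol 4.2, exclusion 17, bars active suicidal thoughts in the past 6 months, so a patient with active ideation at baseline should not be enrolled and most active ideation on treatment would be new. This largely stands. It does not expressly cover a passive wish to be dead, the first ideation item in SAP Table 5. With that item scored 1, the record (1,4,3) would give 3 − 4 = −1 at Week 12 under the SAP rule, against 3 − 1 = +2 from baseline.

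Third, the physical, neurological and developmental examinations are also reported against the previous visit (SAP 4.3.4.2 to 4.3.4.4), and the C-SSRS form itself looks back to the previous visit. Those examination outputs are listings, though, not a change summary, and a form's recall window is not a reference point for change.

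Fourth, new or worsening suicidality reported clinically would be tabulated as a treatment-emergent adverse event (SAP 4.3.2). That is a useful separate route, but it does not summarize the scale.

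Finally, a reader might infer that the C-SSRS percentages are diluted by patients who were never assessed. The default Safety population and the age limit make this possible. But SAP 2.1 summarizes observed data only, Protocol 9.7 limits the change analysis to where it applies, and the adult and pediatric split keeps children under 7 out of the adult table. The denominator is unclear; it has not been shown to be wrong.

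**Conclusion.** The point holds as a choice of comparator and a missing summary. SAP 4.3.6.1 departs from the plan's own pre-dose baseline. As a result, change values after onset can be zero or negative for a patient who remains worse than before treatment: 0 against +4 and −2 against +2 at Week 12 in the two Part A examples. No planned table shows emergence or worsening relative to baseline. The onset visit, the by-visit counts and the listing remain informative, so this is a misleading set of later change rows and not a lost signal.

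The sizes rest on illustrative scores, on reading change as a difference, and on taking Visit 2 as the previous rated visit for Visit 4. No dilution figure is claimed, because the documents do not give the number of patients who will not be assessed.

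**What to change.** In SAP 4.3.6.1, replace the previous-visit reference with change from the pre-dose baseline. Add one shift table of baseline category (none, ideation, behavior, using SAP Table 5) against worst post-baseline category. Present it for Part A, Part B and overall, within the planned adult and pediatric split, with the pre-dose rating as the baseline in every period.

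As a clarification, base that table on patients with a baseline and at least one post-baseline C-SSRS, and print the number not assessed.

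The cost is a change of SAP wording and one extra small table. All the data are already collected, and the by-visit counts and the listing stay as planned.
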